10.6 Deaths

All AEs resulting in death either during the survey period or within 28 days after the last dose of Survey medication must be reported as an SAE within 24 hours of the Investigator's knowledge of the event.

The convention for recording death is as follows:

- AE term: lead cause of death (e.g. multiple organ failure, pneumonia, myocardial infarction).
- Outcome: fatal.
- The **only exception** is if the cause of death is unknown (i.e. sudden or unexplained death), in which case the AE term may be 'Death' or 'Sudden death'.

10.7 Discontinuation/Withdrawal due to Adverse Events/Serious Adverse Events

Discontinuation/withdrawal due to AEs should be distinguished from discontinuation/withdrawal due to insufficient response to the Survey medication (see Sections 6.4.).

If the Survey medication is discontinued due to a SAE it must be reported immediately to the Sponsor's designated representative (see Section 10.4).

In all cases the Investigator must ensure the subject receives appropriate medical follow-up.

10.8 Reporting to Competent Authorities/IECs/IRBs/Other Investigators

The Sponsor will ensure that processes are in place for submission of reports of Suspected Unexpected Serious Adverse Reactions (SUSARs) occurring during the survey to the Competent Authorities (CA), IECs, IRBs and other Investigators concerned by the Survey medication. Reporting will be done in accordance with the applicable regulatory requirements.

11. STATISTICAL CONSIDERATIONS

11.1 Subject Classification and Definitions

- **Treated subject :** Subject who is treated with at least one dose of survey medication

11.2 Analyses Populations Definitions

- **Safety population:** All subjects who received at least one dose of survey medication

11.2.1 *Populations Analysed*

The analyses of safety data will be performed based on the Safety population.

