4. SURVEY DESIGN

4.1 Overview

Centers will prescribe Dysport according to their normal practice. Each center will record the dose of Dysport administered and the condition being treated. At the patients scheduled return to the site (following visit depends on investigator's judgement, it's usually about 4 weeks later), their treating physician will perform an assessment of safety, and details on any adverse events will be collected. Patients who doesn't return to site will be contacted by telephone to ask about any adverse events that they have had since their treatment. These data will be recorded on simple Case Record Forms (CRFs) and returned to Ipsen.

4.1.1 *Population Characteristics*

Patients with Spasticity or Dystonia scheduled to receive Dysport within each participating centre are to be included in this survey.

4.1.2 *Design*

This is an open, non-randomised, multi-centre, non-interventional, post-marketing survey.

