6.4 Discontinuation/Withdrawal Procedures

N/A

7. METHODOLOGY**7.1 Survey Schedule**

The schedule of observations and assessments during the survey are summarised below.

Table 1. Schedule of Observations

	Day 0	Follow-up visit	Telephone contact if no follow up visit

Demography& Eligibility	X		
Treatment injections	X		
Adverse events		X	X

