7.2 Survey Visits

7.2.1 *Baseline (Day 0, visit 1)*

All subjects attending the centre for their normal Dysport treatment will receive Dysport as decided by the treating physician, in accordance with the marketing authorisation. The following details will be recorded on the survey CRF:

- Centre number
- Subject number
- Subject initials,
- Demography
- Previous Toxin history
- Indication
- Dysport administration

7.2.2 *Follow-up visit*

Patients will then return for their normal follow up visit and an assessment of safety will be recorded on the CRF along with any AEs that have occurred since the last treatment.

- Collection of adverse events

7.2.3 *Telephone contact*

Contact will be made with the patient by telephone after planned normal follow-up visit, or if the patient is unavailable to visit. Patients will be asked about any AEs that they may have experienced since they received their Dysport treatment. These AEs will be recorded on the CRF.

7.2.4 *Survey Completion or Withdrawal*

N/A

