11.4 Statistical/Analytical Methods

Statistical analyses will be performed by an external Contract Research Organisation (CRO), managed by the Sponsor's Clinical Development Data Sciences Department.

A Reporting and Analysis plan (RAP) describing the planned statistical analysis in detail with tables, figures and listings (TFLs) templates will be developed as a separate document.

Statistical evaluation will be performed using Statistical Analysis System (SAS)[®].

11.4.1 *Demographic and Other Baseline Characteristics*

Descriptive summary statistics (n, mean, standard deviation (SD), median, minimum, maximum) or demographic and previous toxin medication history will be presented.

11.4.2 *Subject Disposition and Withdrawals*

The numbers of subjects who were treated, discontinued and completed the survey period will be tabulated. Primary reasons for discontinuation of survey treatment will be tabulated.

11.4.3 *Pharmacokinetic Data*

NA

11.4.4 *Efficacy Evaluation*

NA

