11.4.5 Safety Evaluation

All safety data will be displayed in the subject data listings. Analyses and summary tables will be based upon the safety population.

AEs will be coded according to the Medical Dictionary for Regulatory Activities (MedDRA) and will be classified by MedDRA preferred term and system organ class. AE listings will be presented by subject, system organ class and preferred term.

Incidence of all reported AEs/treatment emergent AEs (TEAE) and SAEs will be tabulated. In addition, summary tables will be presented by maximum intensity, drug relationship and AEs/TEAEs associated with premature withdrawal of survey medication.

A TEAE is defined as any AE that occurs during the active phase of the survey if:

it was not present prior to receiving the first dose of Survey medication, or

it was present prior to receiving the first dose of Survey medication but the intensity increased during the active phase of the survey, or

it was present prior to receiving the first dose of Survey medication, the intensity is the same but the drug relationship became related during the active phase of the survey.

Treatment emergent AEs will be flagged (*) in the AEs listings.

Concomitant medication will be coded by using WHO Drug Dictionary and will be summarised with the number and percentage of subjects receiving concomitant medication by drug class and preferred drug name.

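### AE percentages on all treated patients in effect count anyone never reached after injection as AE-free, and the disposition table leaves undefined the terms that would show the loss

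*Protocol*

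**What the plan says.** **Denominator.** Protocol 11.2 defines the safety population as "All subjects who received at least one dose of survey medication" and 11.2.1 adds: "The analyses of safety data will be performed based on the Safety population". The synopsis gives the same all-treated definition. Section 11.4.5 repeats the link for the tables: "Analyses and summary tables will be based upon the safety population".

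**Numerator.** Section 11.4.5 states: "Incidence of all reported AEs/treatment emergent AEs (TEAE) and SAEs will be tabulated".

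**How AEs are obtained.** Table 1 (section 7.1) marks adverse events under the follow-up visit and under the telephone contact, and not on Day 0. Under section 4.1, patients who do not "return to site will be contacted by telephone to ask about any adverse events". Section 8.2.1 also accepts spontaneous reports. No section says how a treated patient with neither visit nor call is classified.

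**Disposition.** Section 11.4.2 plans counts of treated, discontinued and completed subjects, and adds: "Primary reasons for discontinuation of survey treatment will be tabulated". Section 11.4.5 plans a table of AEs linked to premature withdrawal of the medication. Section 10.7 refers the reader to 6.4 for types of withdrawal. Yet "6.4 Discontinuation/Withdrawal Procedures" and section 7.2.4, "Survey Completion or Withdrawal", both read N/A, and Table 1 marks treatment injections on Day 0 only.

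**The concern.** AE collection is the survey's only endpoint (4.2), so the AE percentage is its main result. An all-treated safety set is conventional, and it works well when repeated scheduled contacts mean that nearly every treated patient is assessed. Here elicitation may rest on a single contact, timed by the investigator's judgement and each centre's normal practice. A patient missed at that contact has not been shown to be free of AEs, but the percentage treats that patient as if so.

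The error runs in one direction: the all-treated figure can understate the AE risk but cannot overstate it through non-contact. The disposition table is where a reader would look for the size of the loss. With 'completed' undefined, that reader cannot tell whether it means assessed after injection or something else.

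**Working it through.** **Is there a figure to reproduce?** No. The 500 in section 11.3 is a feasibility number without alpha, power or effect size, and 11.3.1 rules out testing. The check is therefore arithmetic on the planned percentage.

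**Inputs.** Treated patients: 500 (11.3). Unreached fraction L: not in the protocol, assumed 5%, 10%, 20%. True AE risk: not in the protocol, assumed 5%, 10%, 20%.

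**Formula.** Let p_c be the AE risk in patients who are contacted, p_u the risk in those who are not, and s the part of p_u that arrives as spontaneous reports (0 ≤ s ≤ p_u).

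- True incidence = (1 − L) × p_c + L × p_u
- All-treated percentage as planned = (1 − L) × p_c + L × s
- Shortfall = L × (p_u − s), which is never negative and equals L × p_u when s = 0

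**Results with p_c = p_u = p and s = 0**, so the planned percentage is p × (1 − L):

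| L | Not reached, of 500 | p = 5% | p = 10% | p = 20% |
|---|---|---|---|---|
| 0% | 0 | 5.0% | 10.0% | 20.0% |
| 5% | 25 | 4.75% | 9.5% | 19.0% |
| 10% | 50 | 4.5% | 9.0% | 18.0% |
| 20% | 100 | 4.0% | 8.0% | 16.0% |

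**Does an assessed-patient denominator cure this?** Restricted to contacted patients it estimates p_c. Its error is p_c − [(1 − L) × p_c + L × p_u] = L × (p_c − p_u), which can take either sign. At L = 10% and s = 0:

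- p_c = 20%, p_u = 10%: truth = 0.9 × 20% + 0.1 × 10% = 19%. All-treated shows 0.9 × 20% = 18%, assessed shows 20%.
- p_c = 10%, p_u = 20%: truth = 0.9 × 10% + 0.1 × 20% = 11%. All-treated shows 0.9 × 10% = 9%, assessed shows 10%.

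If unreached patients have the same or lower risk, the two columns bracket the truth. If they have higher risk, both fall short, the assessed column by less. Neither column is sufficient alone, and both need the count of patients not reached.

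**Disposition wording side by side.** Sections 11.4.2 and 11.4.5 call for discontinuation, completion and premature-withdrawal outputs, and 10.7 points to 6.4 for the distinction between withdrawals. Sections 6.4 and 7.2.4, where these terms would be defined, are N/A. Treated minus completed would be the natural count of patients without follow-up, but only once 'completed' has a meaning.

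**The case against.** The strongest reply is that an all-treated safety set is standard, that section 11.4 leaves detailed analysis and table templates to a separate Reporting and Analysis Plan, and that nothing forbids a supplementary denominator there. Part of this stands: the all-treated set is not wrong in itself and should stay. But the protocol does not leave the denominator open. It fixes it in the synopsis, 11.2 and 11.4.5, and the conflict between 11.4.2 and the N/A entries lies wholly within the protocol.

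A second reply is that telephone follow-up is specified for non-returners, and that telephone numbers are held on the identification list (6.1). This stands as mitigation. It reduces L, possibly to zero, in which case the two denominators agree.

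A third is that the survey is descriptive and, under 11.3, no basis for definitive conclusions. That limits the consequences, but a descriptive percentage should still separate what was observed from what was not.

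A reader might infer more than the documents support:

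- *That every AE, TEAE and SAE rate is lowered by the full unreached fraction.* Sections 8.2.1 and 10.3 admit spontaneous and volunteered reports, and serious events are notified from the investigator's knowledge of them (10.4.1), so some events can be recorded without the planned contact. Section 7.2.3 can also be read as allowing a call after the visit as well as in place of it.
- *That the disposition table cannot show the loss at all.* It does include a completed count. The defect is the missing definition.
- *That the contacted-only figure should replace the all-treated one.* It overstates incidence if well patients are less likely to return or answer.
- *That this is a single-injection survey, so the premature-withdrawal AE table should go.* Single injection is inferred from Table 1 and never stated. Section 4.3.1 speaks of a last intake and 8.2.1 of a first administration.

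**Conclusion.** The point holds in a limited form. As written, the plan cannot reliably separate patients without an AE from patients not assessed. The all-treated percentage falls short of the true incidence by L × p_u, less whatever is reported spontaneously. With an assumed 20% risk in all patients and no spontaneous reports, that is 1, 2 or 4 percentage points at L of 5%, 10% or 20%. It is zero if every non-returner is reached. The direction follows from the protocol's definitions. The size rests on assumed values for both L and the AE risk, since the protocol gives neither.

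The disposition inconsistency needs no assumption: discontinuation and completion are tabulated but undefined, whether or not repeat treatment is possible. The documents do not support abandoning the all-treated population or deleting the premature-withdrawal table.

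**What to change.** 1. **11.2 and 11.4.5:** keep the all-treated safety population. Beside it, show AE incidence among treated patients with at least one post-injection safety contact (visit or telephone) or a spontaneous AE report. State that this second denominator is also open to informative loss. Patients who qualify only by a spontaneous report enter because they had an event, so give their number separately.
2. **11.4.2:** define 'completed' as a documented post-injection safety contact, and tabulate treated / assessed at visit / assessed by telephone only / not reached.
3. **Reconcile** the discontinuation and premature-withdrawal wording in 10.7, 11.4.2 and 11.4.5 with the N/A entries in 6.4 and 7.2.4 and with Table 1. The sponsor should settle what these terms mean in this survey before deciding whether any of those outputs is empty.

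Cost: a few sentences of protocol text, relabelled disposition rows and one extra column per AE table. The rows rely on the visit or call already planned, provided the CRF records which took place. The downside is slightly higher AE percentages in the added column.

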11.3 Sample Size Determination

This is a Post Marketing Survey with a number of subjects where sample size of 500 was chosen on the basis of practical constraints and not on statistical considerations. Therefore, it is not intended to serve as the basis for definitive conclusions about safety or efficacy.

11.3.1 *Significance Testing and Estimations*

As this is a descriptive (safety and tolerability) survey, no statistical testing will be carried out.

11.4 Statistical/Analytical Methods

Statistical analyses will be performed by an external Contract Research Organisation (CRO), managed by the Sponsor's Clinical Development Data Sciences Department.

A Reporting and Analysis plan (RAP) describing the planned statistical analysis in detail with tables, figures and listings (TFLs) templates will be developed as a separate document.

Statistical evaluation will be performed using Statistical Analysis System (SAS)[®].

11.4.1 *Demographic and Other Baseline Characteristics*

Descriptive summary statistics (n, mean, standard deviation (SD), median, minimum, maximum) or demographic and previous toxin medication history will be presented.

11.4.2 *Subject Disposition and Withdrawals*

The numbers of subjects who were treated, discontinued and completed the survey period will be tabulated. Primary reasons for discontinuation of survey treatment will be tabulated.

11.4.3 *Pharmacokinetic Data*

NA

11.4.4 *Efficacy Evaluation*

NA

11.4.5 Safety Evaluation

All safety data will be displayed in the subject data listings. Analyses and summary tables will be based upon the safety population.

AEs will be coded according to the Medical Dictionary for Regulatory Activities (MedDRA) and will be classified by MedDRA preferred term and system organ class. AE listings will be presented by subject, system organ class and preferred term.

Incidence of all reported AEs/treatment emergent AEs (TEAE) and SAEs will be tabulated. In addition, summary tables will be presented by maximum intensity, drug relationship and AEs/TEAEs associated with premature withdrawal of survey medication.

A TEAE is defined as any AE that occurs during the active phase of the survey if:

it was not present prior to receiving the first dose of Survey medication, or

it was present prior to receiving the first dose of Survey medication but the intensity increased during the active phase of the survey, or

it was present prior to receiving the first dose of Survey medication, the intensity is the same but the drug relationship became related during the active phase of the survey.

Treatment emergent AEs will be flagged (*) in the AEs listings.

Concomitant medication will be coded by using WHO Drug Dictionary and will be summarised with the number and percentage of subjects receiving concomitant medication by drug class and preferred drug name.

11.5 Subgroup Analyses

NA

11.6 Interim Analyses and Data Monitoring

NA

11.7 Final Analysis

NA

12. MONITORING PROCEDURES

The Investigator is responsible for the validity of all data collected at the site. The Sponsor is responsible for monitoring this data to verify that the rights and well being of subjects are protected, that trial data are accurate (complete and verifiable to source data) and that the trial is conducted in compliance with the protocol, GCP and regulatory requirements.

12.1 Routine Monitoring

Sponsor-assigned monitors or representatives will conduct regular site visits. The Investigator will allow direct access to all relevant files (for all subjects) for the purpose of verifying entries made in the CRF and assist with the monitor's

activities, if requested. Adequate time and space for monitoring visits should be made available by the Investigator.

Whenever a subject name is revealed on a document required by the Sponsor (e.g., laboratory print-outs) the name must be blacked out permanently by the site personnel, leaving the initials visible, and annotated with the subject number as identification.

13. SURVEY MANAGEMENT

13.1 Inspections and Auditing Procedures

Authorised personnel from external CAs and Sponsor-authorised Quality Assurance personnel may carry out inspections and audits. The purpose of an audit is to ensure that ethical, regulatory and quality requirements are fulfilled in all studies performed by the Sponsor.

Auditors and inspectors must have direct access to survey documents and site facilities as specified in section 12.1, and to any other locations used for the purpose of the survey in question (e.g., laboratories).

In the event of the site being notified directly of a regulatory inspection, the Investigator must notify the Sponsor representative as soon as possible, to assist with preparations for the inspection.

13.2 Data Recording of Survey Data

In compliance with GCP, the medical records/medical notes, etc., should be clearly marked and permit easy identification of a subject's participation in the specified clinical survey.

The Investigator must record all data relating to protocol procedures, Survey medication administration, safety data and on the CRFs provided for the survey. The Investigator, by completing the signature log, may formally designate authority to complete CRFs to appropriately qualified staff.

The Investigator must sign the End of Survey/ Certification of completion CRF page to attest to the accuracy and completeness of all the data.

All corrections on a CRF and on source documents must be made in a way, which does not obscure the original entry. The correct data must be inserted, dated and initialled/authorised by survey site personnel. If it is not obvious why a change has been made, a reason must be provided.

13.3 Source Data Verification

As required by GCP, the Sponsor assigned monitor must verify, by direct reference to the source documents, that the data required by the protocol are accurately reported on the CRF.

The source documents must, as a minimum, contain the following; a statement that the subject is included in a clinical survey, the identity of the survey, diagnosis and eligibility criteria, visit dates (with subject status), Survey medication administration, and any AEs and associated concomitant medication.

Definition for source data and source documents are given below:

13.4 Data Quality

Monitored CRFs transferred from the investigational site to the assigned Data Management group will be reviewed (secondary monitoring) for completeness, consistency, legibility and protocol compliance.

Reasons should be given on the relevant CRF page for any missing data and other protocol deviations, where space has been provided. Any data management queries and items not adequately explained will be returned to the Investigator by the monitor for clarification/correction. The Investigator must ensure that data queries are dealt with promptly. Copies of all data changes and clarifications must be retained by the Investigator and filed with the CRFs.

13.5 Data Management

Data management will be conducted by a CRO, directed by the Sponsor's Biometrics Group. All data management procedures will be completed in accordance with the CRO's SOPs and IPSEN's requirement.

The Sponsor will ensure that appropriate data entry methods are used (e.g., double data entry) and suitable queries are raised to resolve any missing or inconsistent data.

The Biometrics Group will also ensure that SAE data collected in the CRF is consistent with information provided to the sponsor's pharmacovigilance department (and vice versa).

The coding of an AE, medical history and concomitant medication terms will be performed by the contracted CRO / a CRO, directed by the Sponsor's CDDS Group, and reviewed and approved by the Sponsor. Concomitant medications will be coded using WHODRUG and AEs terms will be coded using MedDRA.

13.6 Survey Management Committees

NA

13.6.1 Data Monitoring Committee

NA

13.6.2 Steering Committee or Operations Committee

NA

13.7 Record Archiving and Retention*

The sponsor, or other owners of the data, shall retain all of the sponsor-specific essential documents pertaining to the trial for five years. The sponsor shall retain all sponsor-specific essential documents in conformance with the applicable regulatory requirement(s) of the country(ies) where the product is approved, and/or where the sponsor intends to apply for approval(s).

If the sponsor discontinues the clinical development of an investigational product (i.e. for any or all indications, routes of administration, or dosage forms), the sponsor shall maintain all sponsor-specific essential documents for at least 5 years after formal discontinuation or in conformance with the applicable regulatory requirement(s).

The sponsor shall inform the investigator(s)/institution(s) in writing of the need for record retention and shall notify the investigator(s)/institution(s) in writing when the trial related records are no longer needed.

* Korea Food and Drug Administration Notification No. 1999-67; KGCP 29

